Project title:

Use of Diced Cartilage for Management of Internal Mammary Vessel Exposure Sites in
Autologous Breast Reconstruction

Date: 10.07.2024

1) Studyprotocol

Procedures for informing and obtaining consent:

The recruited subjects will be informed about the nature, importance, risks (anonymizes data management) and scope of the intended scientific investigation in a personal conversation with one of the investigators and will receive patient information. After sufficient time for reflection, the consent will be confirmed in writing on the form prepared for this purpose - declaration of consent.

Measures:

This retrospective single-center cohort study included all autologous breast reconstructions performed from October 2021 to June 2023, in which diced cartilage (DC) was used to manage internal mammary vessel exposure sites (IMVES). These reconstructions will be divided into two groups: one with prior ipsilateral breast radiotherapy (DCR) and one without irradiation (DC) to evaluate the suitability of irradiated cartilage for the DC procedure. The control group consisted of an equal number of consecutive autologous breast reconstructions performed before the implementation of the DC procedure, for which rib cartilage segments were also removed but IMVES were managed conservatively. Controls will not be recruited during the period of DC use because initially, DC was not used consistently by all team members and may have been avoided in difficult reconstructions limiting the comparability of these patients. Data will be collected using electronic patient records, photographic documentation, and available postoperative MRI of reconstructed breasts.

Magnetic resonance imaging (MRI) scans performed at least 6 months postoperatively will be used to evaluate the sinking depth of epicostal soft tissue into the space of rib segment resection on axial planes (JiveX Software, VISUS Health IT GmbH, Bochum, Germany).

Postoperative photographic images will be examined by two investigators (blinded to group assignments) for IMVES-associated deformities using standardized photographic images of the reconstructed breasts at the 6-month follow-up.

2) Statistical Analysis Plan

Statistical analysis will be performed using IBM SPSS Version 24 (IBM, Somers, NY, USA) and R 4.3.2 (R Core Team). Metrically scaled parameters will be assessed for a normal distribution using Shapiro–Wilk tests. Results for normal data will be presented as mean \pm standard deviation (SD) and will be analyzed using multi-factor variance analysis. Paired t-tests with Bonferroni correction will be used when significant differences were observed. Non-normally distributed metric parameters will be expressed as median (Q25–Q75) values and will be assessed using the Kruskal–Wallis test. Pairwise Mann–Whitney U tests with the Bonferroni correction will be used when significant differences were found. Categorical parameters will be assessed using the Chi-squared or Fisher tests, without tests for normality. Pairwise chi-square tests (or Fisher tests) with Bonferroni correction will be used when significant results were found. MRI data will be analyzed by isolating subgroups of the study population with MRI and applying pairwise case exclusions. A Chi-square test of independence will be performed to determine whether the groups differed significantly with regard to the presence of MRI. In addition, further comparison of the three groups will be carried out for the variables surveyed to clarify group differences. The significance level will be set at $\alpha = 0.05$ for all tests.

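### Breasts, not patients, are counted and tested, and no planned method allows for two breasts from one woman, so p-values are miscalibrated if bilateral cases are included

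*Combined protocol and SAP*

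**What the plan says.** Under Measures in section 1 (Studyprotocol), the study "included all autologous breast reconstructions performed from October 2021 to June 2023, in which diced cartilage (DC) was used". These reconstructions form two groups, "one with prior ipsilateral breast radiotherapy (DCR) and one without irradiation (DC) to evaluate the suitability of irradiated cartilage". The criterion is specific to a side, so it applies to a breast and not to a woman. Controls are counted the same way: "The control group consisted of an equal number of consecutive autologous breast reconstructions performed before the implementation of the DC procedure". Bilateral reconstruction is neither mentioned nor excluded, and nothing limits a patient to one breast.

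Section 2 (Statistical Analysis Plan) says that normal metric data "will be analyzed using multi-factor variance analysis", with the factors unnamed, and then "Paired t-tests with Bonferroni correction will be used when significant differences were observed". Non-normal metric data "will be assessed using the Kruskal–Wallis test", followed by pairwise Mann–Whitney tests with Bonferroni correction. For the rest, "Categorical parameters will be assessed using the Chi-squared or Fisher tests, without tests for normality". There is no mixed model, GEE, clustered variance, patient factor or one-breast rule.

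**The concern.** Two breasts in the same woman share her body habitus, her healing and often the surgeon and the operation, so their outcomes are likely to be correlated. Kruskal–Wallis, Mann–Whitney, chi-squared and Fisher tests assume independent rows.

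The direction of the error depends on where the second breast falls. If both breasts are in one group, that group holds less information than its row count suggests and p-values are too small. If one breast is in DC and the other in DCR, the difference between those groups is more precise than the test assumes and p-values are too large. DC against DCR is the comparison that answers the irradiated-cartilage question. Same-group pairs could produce a false difference there, and split pairs could hide a real one. A reader cannot tell which applies without the number of patients and of each kind of pair.

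**Working it through.** **Inputs.** From the documents: the unit (reconstruction), three groups with controls equal in number to DC plus DCR, the listed tests, and a significance level of 0.05. The documents give no group sizes, bilateral share, within-patient correlation or event rate. The following are therefore assumptions: 60 controls, 30 DC, 30 DCR; *b*, the share of breasts whose partner breast is also in the analysis; and ICC, the within-patient correlation. There is no derived figure in the plan to reproduce, so the check is whether the nominal 5% is kept.

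**Step 1, two groups, normal approximation.** The variance of a difference in means is multiplied by 1 + *b*·ICC if both breasts are in the same group, or by 1 − *b*·ICC if the pairs are split between two equal groups. The true two-sided error is 2 × [1 − Φ(1.96/√factor)].

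- *b* = 0.4, ICC = 0.5, same group: factor 1.20, error 7.4%.
- *b* = 0.4, ICC = 0.5, split: factor 0.80, error 2.8%.
- *b* = 0.2, ICC = 0.2: 5.5% same group, 4.6% split.
- *b* = 0: 5.0%.

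**Step 2, three groups, all pairs in the same group.** The chi-squared critical value on 2 df is −2 ln(0.05), so the true error is approximately 0.05 raised to the power 1/(1 + *b*·ICC).

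- *b* = 0.2, ICC = 0.3: 0.05^(1/1.06) = 5.9%.
- *b* = 0.4, ICC = 0.5: 0.05^(1/1.20) = 8.2%.
- *b* = 0.5, ICC = 0.8: 0.05^(1/1.40) = 11.8%.

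**Step 3, simulation of the planned sequence.** Null hypothesis true, normal outcome, 20,000 replicates per scenario: Kruskal–Wallis at 0.05, then Mann–Whitney at 0.05/3. Triplets are for none / half / all of the DC/DCR pairs split.

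| *b*, ICC | Kruskal–Wallis error | False DC vs DCR claim |
|---|---|---|
| no bilateral patients | 5.1% | 1.5% |
| 0.2, 0.3 | 5.8 / 5.3 / 5.0% | – |
| 0.4, 0.5 | 8.1 / 6.5 / 5.1% | 2.5 / 1.5 / 0.7% |
| 0.5, 0.8 (extreme) | 11.7 / 7.9 / 5.6% | 4.0 / 1.3 / 0.2% |

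The no-split column agrees with step 2. False claims against controls run from 1.5% to 4.0%. With groups of 40/20/20 at *b* = 0.4 and ICC = 0.5, the Kruskal–Wallis error is 7.4 / 6.3 / 5.0%. A three-group chi-squared test at 60/30/30 with an assumed 30% prevalence behaves alike: 5.0% with no bilateral patients, and 8.2 / 6.4 / 4.9% at *b* = 0.4 and ICC = 0.5.

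An overall error near 5% when all pairs are split is not reassurance. In that column the DC against DCR test is clearly too conservative.

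**Step 4, patient-level variables.** The SAP also compares the groups on the surveyed variables and on whether an MRI exists. A variable that belongs to the woman has ICC = 1. MRI presence would be close to that if one scan shows both breasts, which is an assumption. By the step 2 formula, same-group pairs at *b* = 0.2 give 0.05^(1/1.20) = 8.2%, and at *b* = 0.4 they give 0.05^(1/1.40) = 11.8%.

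**The case against.** The strongest reply is that the premise is not documented. Nothing shows that any woman contributes two breasts, and a side-specific radiotherapy criterion does not imply that she does. That is true, and it is why the conclusion is conditional. But a plan that takes all, and consecutive, reconstructions without a one-breast rule admits both sides. Followed as written, it would then test dependent rows as if they were independent.

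A second reply is that the overall test followed by Bonferroni absorbs much of the inflation. The chance of at least one false pairwise claim is about 3.7–3.9% without clustering, 6.5 / 4.7 / 4.0% at *b* = 0.4 and ICC = 0.5, and 4.2–4.6% at *b* = 0.2 and ICC = 0.3. This stands as a limit on the size of the problem. It does not restore the individual comparisons with controls, and it does nothing for a DC against DCR test that is too conservative.

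A third reply is that the unnamed ANOVA factors might include the patient, or that the paired t-tests deal with dependence. The first is not stated and could not help the rank or categorical tests. The second are follow-up tests between groups that are not matched, no pairing by patient is defined, and they cannot handle two breasts in one group.

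**Conclusion.** The concern holds. The plan counts and groups breasts, admits bilateral patients and names no method that uses the patient. If any are included, the p-values are miscalibrated: generally too small against controls, and either too small or too large for DC against DCR according to how the pairs fall. Partial cancellation is possible.

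The size cannot be fixed from the documents. Under the assumptions above, the distortion is slight at a low bilateral share. At a moderate share it matters most when few pairs are split (about 8% instead of 5% overall) or when nearly all are (a DC against DCR claim rate of 0.7% instead of 1.5%). With no bilateral patients there is no error. The plan should be corrected before analysis, but nothing in the design has to change.

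**What to change.** State the unit of analysis and record a patient identifier. Then:

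- Analyse sinking depth and deformity with a patient random intercept, or with GEE using patient-clustered standard errors and a small-sample correction.
- Where counts are small, use a permutation test that moves group labels across whole patients, separately for unilateral and bilateral patients. This also covers a group with no deformities, where logistic GEE has no finite estimate.
- Add a one-breast-per-patient sensitivity analysis and fix in advance how the breast is chosen, since for a split patient that choice decides the group.
- Compare patient-level variables once per patient, with a stated rule for split patients (for example, listing them separately).
- Report patients and breasts per group, with the numbers of same-group and split pairs.

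In simulation, patient-level permutation of the Kruskal–Wallis statistic held the error at 4.4–5.6% (8,000 replicates, 999 permutations, both sets of group sizes). A REML random-intercept F test gave 4.8–6.2%, slightly liberal with few split pairs, hence the small-sample correction. The GEE option was not simulated for a binary outcome.

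The cost is a few lines of SAP text, one extra column in the data set and standard routines in R, which is already planned. Standard errors against controls will be somewhat larger, and those for split DC/DCR pairs smaller. If no patient had both breasts included, one sentence saying so replaces all of this.

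### Diced-cartilage cases are split by prior radiotherapy but the historical controls are not, so comparisons with control mix radiotherapy with technique

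*Combined protocol and SAP*

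**What the plan says.** Under Measures in the Studyprotocol section, reconstructions managed with diced cartilage are separated by radiotherapy history: "one with prior ipsilateral breast radiotherapy (DCR) and one without irradiation (DC) to evaluate the suitability of irradiated cartilage for the DC procedure". DCR is therefore wholly irradiated and DC wholly non-irradiated.

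The comparator is one group: "The control group consisted of an equal number of consecutive autologous breast reconstructions performed before the implementation of the DC procedure". As to technique, the protocol describes these as cases "for which rib cartilage segments were also removed but IMVES were managed conservatively". The group is wholly historical ("Controls will not be recruited during the period of DC use"). Nothing is said about the controls' radiotherapy history, either as a selection rule or as a way of dividing or matching them.

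The Statistical Analysis Plan compares the three groups by an omnibus test followed by Bonferroni-corrected pairwise tests. Normal data "will be analyzed using multi-factor variance analysis", with no factors named. Non-normal metric data go to Kruskal–Wallis and Mann–Whitney tests. For the rest, "Categorical parameters will be assessed using the Chi-squared or Fisher tests". A closing sentence adds a three-group comparison on the surveyed variables. No contrast with irradiated or non-irradiated controls is described.

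**The concern.** DC v control and DCR v control are the comparisons that would show whether diced cartilage helps. Each differs from control in technique and, unless the controls happen to match, in radiotherapy history. If radiotherapy worsens the outcome, a technique that does nothing would tend to look better than control in DC and worse than control in DCR. If radiotherapy improves it, the pattern reverses. A real benefit in irradiated breasts could also be masked. The documents do not say which direction applies, or whether there is an effect.

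The suitability aim is affected too. DCR v DC holds technique constant but cannot tell a problem with reusing irradiated cartilage from a generally different outcome in irradiated breasts. Irradiated controls would supply that reference, and the plan does not use them.

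**Working it through.** **Inputs.** From the documents: three groups, alpha 0.05, an omnibus test, then Bonferroni-corrected pairs (taken as 0.05/3 = 0.0167 for three pairs). The documents state no group sizes, irradiated control share, radiotherapy effect, SD, deformity rate or share with MRI, so there is no planned figure to reproduce. All of these are assumed below.

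**Bias.** Let p be the irradiated share of controls, rho the radiotherapy effect under conservative management, and T1 and T0 the technique effects in irradiated and non-irradiated breasts.

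- Expected DC − control = T0 − p × rho
- Expected DCR − control = T1 + (1−p) × rho
- Expected DCR − DC = rho + (T1 − T0)

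The bias terms in the first two lines have absolute sum |rho|, so at least one control comparison is off by |rho|/2 or more. At p = 0 only DCR v control is biased, and at p = 1 only DC v control. The third line shows why DCR v DC cannot separate the general effect of irradiation (rho) from a different effect of diced cartilage in irradiated breasts (T1 − T0).

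For rho = 0.2–0.8 SD and p = 0.3–0.5, the DC v control bias runs from −0.3 × 0.2 = −0.06 to −0.5 × 0.8 = −0.40 SD. The DCR v control bias runs from 0.5 × 0.2 = 0.10 to 0.7 × 0.8 = 0.56 SD. For deformity at an assumed 20% non-irradiated and 40% irradiated, p = 0.5 gives a control rate of 30% and biases of −10 and +10 points.

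**False control comparisons with an inert technique (simulation).** Outcomes are normal with unit SD, reconstructions are independent and there is no era effect. ANOVA at 0.05 is followed by independent-samples t-tests at 0.05/3, because the groups are different reconstructions. Sizes are DC/DCR/control, and ranges cover p = 0.3–0.5. Two control sizes are shown at 30 per diced-cartilage group because an equal number of controls could be read either way.

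| rho (SD) | 30/30/60 | 30/30/30 | 15/15/30 | 30/30/60, DCR v DC not significant |
|---|---|---|---|---|
| 0 | 3% | – | – | about 2.5% |
| 0.2 | 5% | 4–5% | 4% | 3–4% |
| 0.3 | 8–9% | 6–7% | 5% | 4–5% |
| 0.5 | 17–22% | 14–16% | 9–11% | 5–7% |
| 0.8 | 42–54% | 32–41% | 19–25% | 2–5% |

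The Kruskal–Wallis/Mann–Whitney route at 30/30/60 gives 5%, 7–8%, 16–20% and 40–51% for rho = 0.2 to 0.8 SD. For deformity at 30/30/60 by chi-squared or Fisher, the rates are about 4% (20% v 25%), 6–7% (20% v 30%), 6–8% (10% v 20%) and 14–18% (20% v 40%).

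**Can the planned analysis repair this?** The rank and contingency-table tests take no covariate. The multi-factor ANOVA could include radiotherapy, but the plan does not say so, and it covers normal data only. The extra three-group comparison could reveal p if radiotherapy is a surveyed variable, but it adjusts nothing.

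**The case against.** The strongest reply is that the split does what it was made for. DCR v DC bears on suitability with technique held constant, and the protocol does not set diced cartilage against conservative management within irradiated breasts as an objective. This stands in part: DCR v DC is useful and unaffected by the control mix, but it leaves the two control comparisons uncorrected.

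Second, rho is unknown, and any radiotherapy effect might act only through the reused cartilage. In that case rho among controls is zero and the bias vanishes. That is correct and is the zero case in the algebra above, but the documents give no reason to rely on it.

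Third, the false results often reveal themselves. For p strictly between 0 and 1 the two biases have opposite signs. At 30/30/60 an inert technique made both control comparisons significant in the same direction in at most about 0.1% of simulated studies. DCR v DC is also significant in about a third of the false results at 0.2 SD and in 90–94% at 0.8 SD. This stands as a limit on the harm. It does not cover a real DCR benefit masked by the bias, nor does it correct the estimates.

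Fourth, sinking depth exists only where there is an MRI ("MRI data will be analyzed by isolating subgroups of the study population with MRI and applying pairwise case exclusions"). At 50% MRI coverage the 15/15/30 column is therefore the relevant one. That is fair for this outcome and lowers the error rates.

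Finally, the unnamed ANOVA factors might include radiotherapy. That would still leave non-normal and categorical outcomes unadjusted.

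**Conclusion.** The concern holds, and the plan should be changed. As written, at least one control comparison is biased by half the radiotherapy effect or more whenever radiotherapy affects the outcome under conservative management. That conclusion does not depend on group size or on the controls' radiotherapy mix.

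The practical size is uncertain because it rests on assumed sizes, p and rho. The excess of false findings is slight at 0.2–0.3 SD and becomes large only from about 0.5 SD. It is smaller again in an MRI subset. Confidence in the importance of the point is therefore medium, while confidence in its structure is high.

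**What to change.** Extract prior ipsilateral radiotherapy for every control and report the irradiated share. The source is already in use: "Data will be collected using electronic patient records, photographic documentation, and available postoperative MRI of reconstructed breasts". In the SAP, replace the unspecified multi-factor ANOVA with a named analysis of DC use (yes/no) by radiotherapy (yes/no) for each outcome: a linear or robust model for sinking depth, and a logistic or Firth model for deformity. Report DCR v irradiated controls, DC v non-irradiated controls and the interaction, each with a 95% CI. Base the suitability conclusion on the irradiated-stratum estimate alongside DCR v DC, and call either inconclusive if its interval is wide. State that this removes confounding by radiotherapy only; technique remains confounded with era because all controls predate DC use.

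The cost is one chart variable, SAP wording and some precision. Using half-width = 1.96 × √(1/n1 + 1/n2) SD at 30/30/60 and p = 0.3–0.5:

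- Pooled, 30 v 60: 1.96 × √(1/30 + 1/60) = 0.44 SD.
- DCR v 18–30 irradiated controls: 0.58–0.51 SD, or 33–15% wider.
- DC v 42–30 non-irradiated controls: 0.47–0.51 SD, or 7–15% wider.
- Interaction (summing 1/n over all four cells): 0.72–0.75 SD.

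For sinking depth, divide by the square root of the share with MRI. At an assumed 50%, the half-width is 0.72–0.83 SD for DCR v irradiated controls and 1.01–1.06 SD for the interaction. At 30% these become 0.92–1.07 and 1.31–1.37 SD. The sinking-depth result may well be inconclusive, and the interaction should be read as descriptive.

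### The plan sets out to judge whether irradiated cartilage is suitable but plans only tests of no difference, with no estimate or confidence interval for DCR against DC

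*Combined protocol and SAP*

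**What the plan says.** Section 1 (Studyprotocol, Measures) divides the diced-cartilage cases into those with prior ipsilateral breast radiotherapy (DCR) and those without (DC). The stated reason is "to evaluate the suitability of irradiated cartilage for the DC procedure". A third group, managed conservatively in the period before diced cartilage was introduced, serves as control: "The control group consisted of an equal number of consecutive autologous breast reconstructions". No number is given for any group.

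Section 2 (Statistical Analysis Plan) compares the three groups by analysis of variance, Kruskal–Wallis, or chi-squared or Fisher tests, depending on the data. For every data type the pairwise step depends on the overall result:

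- normal metric data: "Paired t-tests with Bonferroni correction will be used when significant differences were observed"
- non-normal metric data: "Pairwise Mann–Whitney U tests with the Bonferroni correction will be used when significant differences were found"
- categorical data: "Pairwise chi-square tests (or Fisher tests) with Bonferroni correction will be used when significant results were found"

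All tests use a 0.05 level. For the MRI outcome, "MRI data will be analyzed by isolating subgroups of the study population with MRI", so fewer cases may contribute there. Neither section defines suitability, names a margin, or plans an effect estimate or confidence interval for DCR against DC. Neither gives a sample-size or power statement.

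**The concern.** Measured against non-irradiated diced cartilage, suitability is a question of acceptable similarity: is DCR no worse than DC by an amount that matters? A test of no difference can give evidence that the groups differ. It cannot, by failing to reject, give evidence that they are alike. To support a statement about similarity, a reader needs the estimated difference and the range of true differences compatible with the data, and the SAP plans neither.

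What is at stake is the inference about irradiated cartilage. If the DCR–DC comparison comes out non-significant, or is not run because the three-group test was not significant, the plan leaves no inferential result on the stated question. Such an outcome would be compatible with close agreement and also with a sizeable disadvantage for DCR.

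**Working it through.** The plan states no sample size, power, SD or event rate, so it has no figure of its own to reproduce.

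**Inputs from the documents.** Three groups, hence three pairs; level 0.05; Bonferroni correction; controls equal in number to all diced-cartilage cases together. Per-pair level: 0.05/3 = 0.0167.

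**Assumptions.** Two-sided tests; DC and DCR equal in size at 20, 30 or 40 each, so 40, 60 or 80 controls; independent observations; the pairwise t-test taken as a two-sample test, because the groups are different reconstructions. The deformity rates and SD-unit differences are chosen for illustration.

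**Step 1: how often the planned rule flags a true DCR–DC difference.** A difference counts as flagged when the three-group test has p<0.05 and the DCR–DC test has p<0.0167. Metric rows are simulated. Deformity rows combine simulation with exact enumeration of the binomial outcomes; where the two differ, a range is shown.

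| True state | 20 per group | 30 per group | 40 per group |
|---|---|---|---|
| 0.5 SD, controls level with DCR or halfway between | 18% | 30% | 41% |
| 0.8 SD, controls at 1.2 SD | 51% | 73% | 86% |
| Deformity 10% DC, 30% DCR, 40% controls; Fisher | 9–10% | 22–23% | 33–34% |
| Same rates; chi-square | 17–19% | 32% | 43–44% |

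**Step 2: what the conditional step adds.** For 0.5 SD with controls level with DCR, the rule flags 18.6%, 30.2% and 41.6%. The Bonferroni-corrected test alone flags 19.4%, 30.7% and 42.1%. The loss is 0.8, 0.5 and 0.5 points. With controls halfway it is at most about 1.5 points, and in the deformity scenario it is essentially zero. Assumed sample size and the Bonferroni threshold account for nearly all the misses.

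**Step 3: the precision an interval would show.** Large-sample 95% half-widths for DCR minus DC with n per group:

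- Rates of 10% and 30%: 1.96 × √[(0.10×0.90 + 0.30×0.70)/n] = 1.96 × √(0.30/n), which is 24.0, 19.6 and 17.0 percentage points.
- Rates of 10% in both groups: 1.96 × √(0.18/n), which is 18.6, 15.2 and 13.1 points. Even identical observed rates would leave open a DCR disadvantage of roughly that size.
- Metric outcome in SD units: 1.96 × √(2/n), which is 0.62, 0.51 and 0.44. For MRI sinking depth, n is the number with MRI.

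**Step 4: what a formal claim would need.** With one-sided 0.025, 80% power and no true difference, n per group = 2 × (1.96 + 0.84)²/margin² ≈ 15.7/margin². For assumed margins of 0.3, 0.5 and 0.8 SD this gives 175, 63 and 25. The documents name no margin; these figures only show scale.

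**The case against.** Several stronger readings are tempting, and the documents do not support them.

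- *A reader might infer that the investigators will treat p>0.05 as proof of suitability.* Neither section says so. The plan has no decision rule at all, and it speaks of evaluating suitability, not of showing it.
- *A reader might infer that the DCR–DC contrast disappears when the three-group test is not significant.* That goes too far. The SAP presents means with SD or medians with quartiles, and it adds an unconditional further comparison of the three groups on the variables surveyed. DCR and DC values would probably stand side by side. What is missing is an interval for their difference; the further comparison is not specified and promises none.
- *A reader might blame the conditional testing for missed differences.* Step 2 shows that it costs about 0 to 1.5 points.
- *A reader might assume that the study is small and that a clear disadvantage would usually be missed.* No number is stated. At 30 or 40 per group, a 0.8 SD difference would more often be flagged than missed.

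It is also fair to say that suitability might mean improvement over conservative management, for which DCR against control is a natural difference test. That comparison has value, but it does not tell the reader whether irradiated cartilage performs like non-irradiated cartilage.

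What stands after all this is that a non-significant difference is not evidence of similarity, whatever the sample size, and that no planned output would supply such evidence.

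**Conclusion.** The point holds in a limited form. As written, the plan cannot support a conclusion that irradiated cartilage is suitable relative to DC, because every inferential comparison is a test of no difference and no estimate or interval for DCR minus DC is planned. This does not depend on sample size.

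The practical size does depend on it and can only be illustrated. At the assumed 20 to 40 per DC-era group, the rule flags a 0.5 SD difference in fewer than half of studies, and likewise a rise in deformity from 10% to 30% with either test. It flags a 0.8 SD difference in about half to 86%. These figures rest on assumed sizes, equal DC and DCR groups, and assumed rates and control levels. This is a cheap improvement to the SAP, not a flaw that invalidates the study.

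**What to change.** Add to Section 2:

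1. DCR minus DC will be reported with a 95% CI whatever the three-group result: a risk difference for photographic deformity, and a mean or median difference for MRI sinking depth, with the number contributing in each group.
2. A p-value above 0.05 will not be taken as evidence of suitability. The conclusion will be worded by the largest disadvantage of DCR that the interval does not exclude.
3. The conclusion will be labelled exploratory unless the investigators prespecify, with a reason, what difference counts as acceptable on a named outcome.

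A comparison of DCR with irradiated controls could be reported in the same way, but only if radiotherapy status is available for the controls; the documents do not define that subgroup.

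The cost is a few SAP sentences and one table row per outcome, with no new data. The downside is that the suitability conclusion may have to be worded more cautiously.

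### Every control precedes every diced-cartilage case, so the control contrast is fully confounded with calendar period, and the SAP makes no use of operation date

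*Combined protocol and SAP*

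**What the plan says.** Under Measures in the study protocol, the study "included all autologous breast reconstructions performed from October 2021 to June 2023, in which diced cartilage (DC) was used". These cases are split by prior ipsilateral radiotherapy into an irradiated group (DCR) and a non-irradiated group (DC). For the comparator, "The control group consisted of an equal number of consecutive autologous breast reconstructions performed before the implementation of the DC procedure". Concurrent controls are ruled out with a reason: "Controls will not be recruited during the period of DC use because initially, DC was not used consistently by all team members" and it "may have been avoided in difficult reconstructions limiting the comparability of these patients". The start and end dates of the control series are not given, nor is the number of cases.

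The Statistical Analysis Plan compares the three groups. Normally distributed measurements "will be analyzed using multi-factor variance analysis", with the factors unnamed. Non-normal measurements "will be assessed using the Kruskal–Wallis test", followed by pairwise rank tests. "Categorical parameters will be assessed using the Chi-squared or Fisher tests, without tests for normality". Pairwise tests with Bonferroni correction follow a significant overall result. The variables surveyed are also compared across the three groups. Operation date, calendar period, learning curve, trend and time-related sensitivity analysis are not mentioned.

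**The concern.** The reason given for historical controls is a fair answer to selection: concurrent controls might have been the harder cases. It does not address what that choice costs, which is that group membership is determined entirely by when the patient was operated on. If results were changing gradually for other reasons, such as growing experience with vessel exposure, smaller rib resections or better closure, a before-after difference would appear even if diced cartilage did nothing.

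The planned tests would not show this. Chi-squared, Fisher and rank tests take no covariate. The variance analysis could in principle include time, but nothing says that it does. Comparing surveyed variables between groups cannot reveal a slope within the control series. At stake is the contrast on which any claim of benefit from diced cartilage rests.

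**Working it through.** The plan states no sample size, event rate, effect size or drift, so there is no figure of its own to reproduce.

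**Inputs**
- From the protocol: October 2021 to June 2023, counted inclusively, is 21 months; all controls come earlier; group sizes are equal (controls v all diced-cartilage cases).
- From the SAP: α = 0.05, overall test, then Bonferroni pairwise tests.
- Assumed for illustration: control deformity rate 30%; drift of 3 to 5 points a year downwards; control window L = 21 months, varied from 6 to 42; adjoining windows with even accrual; 60 or 100 controls; diced-cartilage cases split equally into DC and DCR; three pairwise comparisons; two-sided tests.

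**1. Gap between the groups.** The midpoints lie (L + 21)/2 months apart.
- L = 21: 21 months = 1.75 years.
- L = 6: 13.5 months = 1.125 years.
- L = 42: 31.5 months = 2.625 years.

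**2. Spurious difference = drift × gap.**
- L = 21: 3 × 1.75 = 5.25; 4 × 1.75 = 7.0; 5 × 1.75 = 8.75 points.
- Over L = 6 to 42: from 3 × 1.125 = 3.4 to 5 × 2.625 = 13.1 points.

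**3. Chance of a significant control contrast with no effect of diced cartilage.** Simulation of the planned sequence (three-group chi-squared at 0.05, then pairwise chi-squared at 0.05/3), L = 21:

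| Controls | Overall test rejects, drift 3-5 points/year | Control v DC or control v DCR significant, drift 3-5 points/year | Same, no drift |
|---|---|---|---|
| 60 | about 7-14% | about 5-10% | about 3% |
| 100 | about 10-22% | about 7-17% | about 3% |

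**4. Can a date term separate technique from time?** Only partly. With two adjoining windows of equal length, the correlation of group with date is 0.866, so R² = 0.75 and the variance inflation is 1/(1 − 0.75) = 4; the standard error of the step doubles. For L from 6 to 42 months the inflation is 3.3 to 4.0. The adjustment works if drift is linear. For a continuous outcome drifting 0.01 SD a month (two-group comparison, 50 per group, L = 21), the false-positive rate falls from 0.19 to about 0.05 and the bias from 0.21 SD to about 0.

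**5. How precise is the slope among controls?** Its standard error is √(0.30 × 0.70 / n) divided by the SD of date, 1.75/√12 = 0.505 years.
- n = 60: √(0.21/60) = 0.0592; 0.0592/0.505 = 0.117, or 11.7 points a year; 95% CI about ±23 points.
- Power to detect 3 to 5 points a year is about 6-7% at n = 60 and 6-9% at n = 100.

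**6. Should the adjusted step decide attribution?** With no drift and a true fall from 30% to 20% at 60 per group, the unadjusted standard error is √((0.21 + 0.16)/60) = 0.0785, and about 0.157 after adjustment. The adjusted step then has the wrong sign with probability Φ(−0.10/0.157) ≈ 0.26; simulation agrees.

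**The case against.** The strongest reply is that this is the ordinary limitation of a before-after design chosen for a stated reason. The protocol also specifies consecutive controls, standardized photographs at 6 months and two blinded assessors. Those features limit drift in photography and assessment, and the comparison of surveyed variables may expose measured shifts in case mix. All of that stands, but none of it removes a real change in surgical results over time.

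A reader might infer a larger error rate. A plain two-group test at 0.05 under the same assumptions rejects in 10-20% (60 v 60) or 13-30% (100 v 100). The SAP does not plan that test. It plans three groups and Bonferroni follow-up, which roughly halves those figures. With 60 controls and 3 points a year, the chance of a significant control contrast is about 5%, higher than the 3% without drift but not above the nominal level.

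A reader might also take 21 months as the documented gap between groups. It is documented only as the diced-cartilage window. Since early use was inconsistent, an equal number of consecutive controls could span a shorter period.

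Finally, the proposed check is weak, and sinking depth is known only for patients with MRI, so its slope rests on fewer cases still. This argues against using the check as a decision rule. It does not argue against reporting it.

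**Conclusion.** The concern holds as a matter of design: the control contrast is fully confounded with calendar period and the SAP does nothing to examine it. Nothing in the documents shows that drift occurred, and they do not support any particular size for it. The 5.3 to 8.8 points (3.4 to 13.1 over control windows of 6 to 42 months) and the 5-10% and 7-17% error rates rest on the assumed event rate, drift, sample size, group split and number of comparisons. Bonferroni correction reduces how often a spurious difference is declared significant but leaves the difference itself unchanged. DC v DCR is not touched. The historical controls need not be abandoned; an unexamined before-after difference should not be presented as the effect of diced cartilage.

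**What to change.** Keep the controls and add the following to the protocol and SAP:

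1. State the start and end dates of the control series.
2. Plot deformity and sinking depth by operation date, and report the slope within the control period with its 95% CI.
3. As a pre-specified sensitivity analysis, report the diced-cartilage v control difference from a model with a linear operation-date term, with its 95% CI, beside the unadjusted figure.
4. Describe the control contrast as a before-after difference that may include drift.
5. Do not make attribution depend on the slope or on the direction of the adjusted step. With the imprecision shown above, such a rule would often discard a real effect.

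The cost is SAP wording and a little analysis, since operation dates are already needed to form the groups. The drawbacks should be stated with the results: the adjusted step has about twice the standard error and assumes linearity, and the control slope is too imprecise for a null finding to rule out drift.
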